6.5.1.4 Examination of Subgroups of the Primary Clinical Endpoint

There are no subgroup analyses planned for the primary clinical endpoint.

6.5.2 Analyses of Secondary Clinical Endpoints

6.5.2.1 Sustained unresponsiveness or natural tolerance

The proportion of subjects who experience sustained unresponsiveness in the intervention arm (ability to consume 9043 mg of peanut protein at the SU DBPCFC visit) will be compared to the proportion of subjects who achieve natural tolerance in the control arm (ability to consume 9043 mg of peanut protein) in an intent-to-treat analysis using a continuity corrected chi-squared test. Given success on the desensitization DBPCFC, we anticipate that missing data for the SU DBPCFC visit

will be extremely low. However should the unexpected occur, missing values will be imputed as failures.

6.5.2.2 Immunological parameters

The skin prick test mean wheal diameter will be defined as the difference between the mean wheal diameter for the undiluted peanut extract and the negative control. Changes in skin prick test mean wheal diameter will be compared between randomization groups using linear mixed effects models for data collected at baseline and the desensitization DBPCFC visit. The analysis will include a random subject effect and the fixed effect of randomization assignment, continuous time, and their interaction. Spline models may be considered if the curves exhibit nonlinear trends.

Missing data of the skin prick endpoint will not be imputed. The linear mixed effects model has the advantage that the estimation of the model parameters will be unbiased even in the presence of missing outcomes, assuming that the missing values depend only on the observed values (MAR). If the MAR assumption is not plausible, pattern-mixture modeling (which stratifies subjects by their pattern of missing data) will be used. The All Available Data population will be used for this analysis.

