### 8.2 Screening/Baseline Visit

The purpose of the screening period is to confirm eligibility to continue in the study. The procedures involved in the screening/baseline visit will determine if the participant can be randomized to the study intervention or will be characterized as low threshold (LT) peanut allergy or not peanut allergic (NPA). Those who are LT or NPA will participate for mechanistic studies but will not continue to the randomized trial.

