### AADCRC

The following procedures, assessments, and laboratory measures (windows for sample collection are detailed in the MOP as applicable) will be conducted, some of which to determine participant eligibility for the randomized trial:

- Physical exam, vital signs, complete medical history
- Spirometry (or peak flow under age 7 or if spirometry not allowed per COVID protocols)
- DBPCFC to peanut per modified PRACTALL (and associated examinations)
- Skin prick test to peanut
- Blood samples (before DBPCFC commences and 2 and 4 hours after starting; not to exceed 5cc/kg on a single day or 9.5ml/kg over any eight-week period per NIH guidelines). A saline lock may be placed to facilitate blood sampling at this and other visits where periodic samples are obtained.
- Quality of life survey, diet questionnaire, demographics
- Urine pregnancy if child bearing potential
- Saliva and stool collection

Screening takes place over 3 days (with one DBPCFC per day for 2 days). Each day is 4-8 hours.

If a participant reacts during the placebo arm of a DBPCFC, the DBPCFC may be repeated once. If a determination of reaction cannot be made due to unwillingness to repeat the DBPCFC or repeated placebo reactions, participation will end and any associated data will not be included in the analyses.

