# **13.4.4** Analyses of Secondary and Other Endpoint(s)/Outcome(s)

*Sustained unresponsiveness or natural tolerance*: The proportion of children who experience SU in the active arm of the HT group will be compared to the proportion of children who achieve natural tolerance in the control arm in an intent-to-treat analysis using a continuity corrected chi-squared test, similar to the plan detailed for the primary endpoint.

*Immunological parameters*: Changes in skin prick test mean wheal diameter will be compared between randomization groups using linear mixed effects models for data collected at baseline and desensitization DBPCFC. The linear mixed effects model has the advantage that the estimation of the model parameters will be unbiased even in the presence of missing outcomes, assuming that the missing values depend only on the observed values (MAR). If the MAR assumption is not plausible, pattern-mixture modeling (which stratifies subjects by their pattern of missing data) will be used.

**Quality of life**: Changes in quality of life over the study as measured by The Food Allergy Quality of Life-Parental Burden will be compared between randomization groups and analyzed using linear mixed effects models as described previously (Immunological parameters, above).

**Adverse Events**: Adverse events (AEs) will be coded using the CTCAE, Common Terminology Criteria for AE, V4.0. Individual adverse events will be summarized as the number (%) of events and number (%) of patients with the event in each group. Adverse events will be modelled using Poisson regression and the rate of individual adverse events will compared between randomization arms over the study period. **Long-term adverse events** will be evaluated with data up to 96 weeks for those in the active group who are tested for SU following a desensitization DBPCFC.

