3.1.2 Randomization and Masking

Children age 4-14 years with high threshold peanut allergy will be randomly assigned (1:1) to ingest a sub-threshold amount of peanut daily or to follow avoidance. Randomization will be stratified by age ($4 - \langle 10 \rangle$ years of age vs. 10 - 14 years of age) and cumulative reaction dose at baseline DBPCFC (443mg; 1043 mg; 2043 mg; 5043 mg). The data and statistical coordinating center (DSCC) will maintain control of stratification and randomization. Randomization will be performed centrally through a Web-based data collection system that automates the delivery of the randomization assignments. Neither the participant nor the investigators will be blinded to randomization assignment. The study staff conducting the DBPCFCs, however, will be blinded to the participant randomization status. Trial oversight will be provided by an independent Data and Safety Monitoring Board (DSMB).

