6. STATISTICAL METHODOLOGY

6.1 General Principles

Continuous variables will be summarized using the following descriptive statistics: number of non-missing values, means, standard deviations, medians, interquartile range, maximum, and minimum. Categorical variables will be summarized using number of non-missing values, counts and percentages.

For any variable measured at multiple points in time, change from baseline will be calculated as the difference between the value of the variable at a specific point in time (e.g. 1 year) minus the baseline value. Relative change from baseline will be calculated as the value of a parameter at a specific point in time minus the baseline value of the parameter divided by the baseline value of the parameter. Percent change will be calculated as the relative change multiplied by 100.

All hypothesis testing will be conducted at the 0.05 two-sided significance level unless otherwise specified. P-values will be rounded to three decimal places. P-values less than 0.001 will be reported as <0.001 in tables. P-values greater than 0.999 will be reported as >0.999.

Should any of the statistical methods proposed prove unsuitable during data analysis, more appropriate methods will be used. These include data transformation (for example to a logarithmic scale) to satisfy model assumptions such as normally distributed residuals with constant variance, the application of non-parametric techniques or the use of a different link function or modeling technique.

Additional ad-hoc analyses may be conducted as deemed appropriate.

All analyses will be conducted using SAS V9.4 or higher and R statistical software (version 4.2.2 or higher).

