6.5.1.2 Analysis of Primary Clinical Endpoint

The primary clinical endpoint of this study is the ability to tolerate a dose at least 2 steps higher than the one tolerated at baseline or 9043 mg of peanut protein by the desensitization DBPCFC. The null hypothesis is that there is no difference in the probability of participants who can consume higher amounts of peanut between subjects randomized to ingestion compared to subjects randomized to avoidance. The proportion of subjects in the intervention and the control group meeting the primary outcome will be compared using a continuity corrected chi-squared test at the 0.05 significance level.

As the intent-to-treat principle includes all randomized subjects in the primary analysis, patients who are missing the trial's primary endpoint will have their outcome imputed using multiple imputation assuming that the data are missing at random (MAR). The imputation model will be stratified by randomization assignment and include age, sex, baseline reactive dose strata, clinical severity during baseline DBPCFC as well as peanut-specific IgE levels (log transformed) at baseline and week 16. Since the model includes a mixture of variables types (i.e. continuous and discrete), a fully conditional specification method will be used.²¹ The imputation process will be repeated 30 times to achieve maximal stability of

the procedure. A separate analysis will be conducted for each completed-andimputed dataset. Rubin's rule²² will be used to combine the 30 analyses and test the difference in success rates between the intervention and control groups.

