6.5.1.3 Sensitivity Analysis of the Primary Clinical Endpoint

Sensitivity analyses will be performed to assess the sensitivity of the primary analysis results to choice of statistical test and missing imputation procedure as well as departures of the MAR assumption and to treatment cross-overs, if necessary. Sensitivity analysis include:

- a. Stratified Chi-square test (by baseline reactive dose and age strata)
- b. Fisher's exact test under 5 ad-hoc imputation strategies: i) all are failures, ii) are all failures except the highest dose at baseline which are successes, iii) all are failures except highest two doses at baseline, iv) all are successes except lowest dose at baseline, and v) all are successes. That is, the first and last of the five are the least conservative, respectively, and the others are in between but use the baseline dose as a means of an intermediate approach, which also incorporates a possible difference in distribution of baseline doses between the groups.
- c. If the MAR assumption is not tenable, statistical methods that assume missing not at random (MNAR) such as pattern mixture models for non-ignorable missing data will be considered.
- d. When cross-over rates are high, the ITT effect of being assigned to treatment may differ from the effect of actually receiving treatment. If cross-over rates are high, instrumental variable analysis will be performed to obtain an unbiased estimate of the treatment effect, using randomization assignment as the instrument.
- e. Given the potential impact of COVID-19 pandemic on subject's return for the desensitization DBPCFC visit, a logistic regression model examining the effect of peanut ingestion on success of the primary endpoint will be conducted and adjusted for time from randomization to desensitization DBPCFC visit and whether patients were randomized prior to study pause in March 2020.

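### Free improvement: dropping the arm main effect from the wheal-size and quality-of-life mixed models would narrow their intervals, because randomisation already equates the baseline means in expectation

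*SAP*

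**What the plan says.** SAP 6.5.2.2 analyses wheal size at baseline and at the desensitization DBPCFC. SAP 6.5.2.3 analyses quality of life at those two visits and week 16. Both give the same terms: "The analysis will include a random subject effect and the fixed effect of randomization assignment, continuous time, and their interaction". Both allow splines for non-linear trends and pattern-mixture models if missing at random is implausible. Protocol 13.4.4 says that wheal changes "will be compared between randomization groups using linear mixed effects models for data collected at baseline and desensitization DBPCFC"; it applies the same method to quality of life and lists no model terms.

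Both measures are taken at the screening/baseline visit (Protocol 8.2 and Table 2). That visit's procedures "will determine if the participant can be randomized to the study intervention", and they include the peanut skin prick test and "Quality of life survey, diet questionnaire, demographics".

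Randomisation is stratified by age group and baseline reaction dose (SAP 3.1.2). Neither model contains these factors. For the primary endpoint, the imputation model is "stratified by randomization assignment and include age, sex, baseline reactive dose strata", and one sensitivity test is stratified by both.

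SAP 6.1 says that "change from baseline will be calculated as the difference between the value of the variable at a specific point in time" and the baseline value, but no such time point is named for these two models. Table 2 puts the endpoint visit at week 32, 56, 64 or 72, and Protocol 8.5 lets it run up to 6 months late.

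**The concern.** When baseline is one of the outcome rows, the arm main effect is the difference between arms at time zero. Both measures precede randomisation, so that difference is zero in expectation. The planned model spends information estimating it and passes the resulting noise to the arm-by-time contrast, the quantity of interest. The random subject effect does use each child's baseline, but less efficiently than a model with one baseline mean for both arms.

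What is at stake is the width of the intervals for two named secondary endpoints. SAP 6.6 treats secondary p-values as descriptive, so the estimate and its interval are the main result. A smaller gap lies beside this: with continuous time and no named week, the reader is not told where the fitted arm difference will be read.

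**Working it through.** **The plan's own figure.** The only power statement concerns the primary endpoint. Attenuation: 0.80 × 55 + 0.20 × 10 = 46%, and 0.95 × 10 + 0.05 × 55 = 12.25%. With 36 per arm, the continuity-corrected chi-squared test has 84.2% power by formula and 85.9% by exact enumeration, so the stated 85% reproduces. Nothing below touches it. The documents give no SD, correlation or power for wheal size or quality of life.

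**Set-up.** n = 36 per arm (SAP 6.5.1.1). Assumed: total SD 1; random intercept with correlation ρ between any two measurements on one child; endpoint week w equal to 32, 56, 64 or 72 in equal shares in both arms. Mean of w: m1 = 224/4 = 56. Mean of w²: m2 = (1024 + 3136 + 4096 + 5184)/4 = 3360.

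**Wheal size, rows (0, w).** Generalised least squares variance of the arm-by-time coefficient:

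- common baseline mean: 2(1 − ρ²)/(n·m2)
- baseline means free by arm: 2(1 + ρ)/(n·[m2/(1 − ρ) − m1²/2])
- ratio, common to free: 1 − (1 − ρ)·m1²/(2·m2) = 1 − 0.4667(1 − ρ)

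If every child had the same endpoint week, the ratio would be (1 + ρ)/2.

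**Quality of life, rows (0, 16, w).** The ratio is 1 − A²/(B·C), with A = 72/(1 + 2ρ), B = 3/(1 + 2ρ) and C = [3616 − 5408ρ/(1 + 2ρ)]/(1 − ρ). Here 72 = 16 + 56, 3616 = 16² + 3360 and 5408 = 256 + 32 × 56 + 3360. This reduces to 1 − 1728(1 − ρ)/(3616 + 1824ρ).

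| ρ (assumed) | 0.3 | 0.5 | 0.7 | 0.9 |
|---|---|---|---|---|
| Wheal: variance ratio | 0.67 | 0.77 | 0.86 | 0.95 |
| Wheal: variance saved | 33% | 23% | 14% | 5% |
| Wheal: interval narrower by | 18% | 12% | 7% | 2% |
| Wheal: children per arm matching 36 as planned | 24 | 28 | 31 | 34 |
| Quality of life: variance ratio | 0.71 | 0.81 | 0.89 | 0.97 |
| Quality of life: variance saved | 29% | 19% | 11% | 3% |
| Quality of life: interval narrower by | 16% | 10% | 5% | 2% |
| Quality of life: children per arm matching 36 as planned | 26 | 29 | 32 | 35 |

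Interval narrowing is 1 − √ratio; matching children are 36 × ratio.

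**Example: wheal at week 56, ρ = 0.5.** Common mean: 56² × 2 × 0.75/(36 × 3360) = 0.0389, SE 0.197, 95% half-width 0.39 SD. Planned model: 0.0389/0.7667 = 0.0507, SE 0.225, half-width 0.44 SD. Across the four correlations the half-widths are 0.52/0.44/0.34/0.20 as planned against 0.43/0.39/0.32/0.19.

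**Other schedules.** The schedule above, all visits at week 72, and all visits 26 weeks later were each run with 0 or 15% of endpoints missing at random. The saving ranges over 29–35/21–25/12–15/4–5% (wheal) and 24–29/16–19/9–11/3% (quality of life). With estimated covariance (REML, 1,000 simulated trials per setting, no missing data), rejection under no effect was 3.4–5.7% for all models.

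**Strata.** Added to the planned model, they give a variance ratio of 0.99–1.00. Added to the common-mean model and assumed to explain 10% of variance, they move the wheal ratios to 0.63/0.74/0.84/0.95 and those for quality of life to 0.66/0.78/0.88/0.96.

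**Limits of the model.** A further simulation (1,000 trials, no arm effect) used a between-child SD of 1 and residual SD of 0.5, so ρ = 1/1.25 = 0.8. With unmodelled random slopes (SD 0.5), rejection was 6.5% as planned and 6.4% with a common mean. The gain shrank: the empirical SE went from 0.239 to 0.234, while the common-mean model reported 0.219. When visit time in the intervention arm also tracked the child's own slope (correlation 0.7), a false slope difference of about 0.09 appeared in both models, with rejection of 8.8% and 9.2%.

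**Reporting week.** Under a linear model the same slope reads 72/32 = 2.25 times larger at week 72 than at week 32. The standard error and interval scale by the same factor, so the test is identical.

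**The case against.** The planned model is a recognised way to compare change. No sample-size claim rests on these endpoints, and their p-values are descriptive. The gain depends wholly on a correlation that the documents do not give, and it is negligible at 0.9. Equal visit shares are an assumption too. The weightier threat is endpoint timing: Protocol 13.3 lets the child's progress set it in the intervention arm and a random draw set it in controls, and a common baseline mean does not cure that.

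All of this stands, and it limits the point to a free improvement. It does not remove the gain, which comes from a fact the design guarantees.

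Three stronger readings are tempting, and the documents do not support them:

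- A reader might infer that leaving out the strata causes the loss. It does not: the contrast is essentially within-child, so strata main effects barely alter it.
- A reader might infer that the missing week costs efficiency or could change significance. Under the linear model it only rescales the result, and the slope difference is itself a defined contrast. The gap is one of reporting.
- A reader might infer that the planned analysis is invalid. Nothing here shows inflated type I error under its stated assumptions.

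**Conclusion.** The wheal-size and quality-of-life models estimate a baseline arm difference that randomisation makes zero in expectation. A common baseline mean would cut the variance of the arm-by-time contrast by about 33/23/14/5% (wheal) and 29/19/11/3% (quality of life) at assumed within-child correlations of 0.3/0.5/0.7/0.9. Those sizes also assume a random intercept and endpoint visits shared equally over weeks 32, 56, 64 and 72. The gain is material at 0.3 to 0.7, trivial at 0.9, and smaller if children's slopes vary.

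Neither model should be called valid without conditions. Both assume linear change, a random intercept and data missing at random, and both remain open to bias if visit timing follows the child's own course in one arm only. The consequence is confined to precision for two secondary endpoints.

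**What to change.** In SAP 6.5.2.2 and 6.5.2.3, specify a random subject effect with fixed effects of continuous time and the assignment-by-time interaction, and no main effect of assignment, so that both arms share one baseline mean. If splines are used, every term involving assignment should be zero at baseline. Confirm that the baseline survey and skin test are recorded before assignment is known.

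Age group and baseline reaction dose may be added for consistency with the design, at a cost of 4 degrees of freedom (1 + 3), but little precision should be expected from them.

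Name before data lock the week at which the fitted arm difference in change and its 95% CI are read, for example the mean endpoint week (56 if the four visit weeks are equally common). State the linearity, random-intercept and missing-at-random assumptions, and note that the common mean does not address timing driven by the child's progress.

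The cost is a few sentences of SAP text. No new data are needed, and the common mean adds no assumption beyond randomisation. Protocol 13.4.4 lists no model terms, so no protocol amendment is required, and the SAP's opening statement permits revision before data lock.

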6.5.2.3 Quality of life

Changes in quality of life over the study as measured by The Food Allergy Quality of Life-Parental Burden²³ will be compared between randomization groups and analyzed using linear mixed effects models for data collected at baseline, week 16, and the desensitization DBPCFC visit. The analysis will include a random subject effect and the fixed effect of randomization assignment, continuous time, and their interaction. Spline models may be considered if the curves exhibit non-linear trends. If the MAR assumption for linear mixed models is not plausible, pattern-mixture modeling will be used. The All Available Data population will be used for this analysis.

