6.5 Primary and Secondary Clinical Endpoint Analyses

6.5.1 Analysis of the Primary Clinical Endpoint and Determination of Sample Size

6.5.1.1 Determination of Sample Size

For sample size calculations, we assume a conservative estimate for the proportion of spontaneous tolerance in the control group of 10%. We believe that an additional absolute increase of 45 percentage points under the intervention is feasible and clinically meaningful (55% vs. 10%). We also assume a drop-in rate (avoiders to consumers) and drop-out rate (consumers discontinuing study treatment) of 5% and 20%, respectively. This results in an attenuated effect size of 33.75% percentage points (46% vs. 12.25%. A total of 72 children randomized with equal probability to the active or control arm (36 per group) provides approximately 85% power to detect a difference of 33.75% (46% versus 12.25%) in the proportion of children who tolerate at least 2 steps higher amount from baseline or the full amount of peanut protein by the desensitization DBPCFC visit, based on a 0.05 level continuity corrected chi-squared test. We believe the drop-in rate will be kept at a minimum since parents and children will likely not attempt dose escalation on their own. Peanut-specific IgG levels will be monitored in all participants and those with rising peanut-specific IgG from ingestion could be identified. The drop-out rate is conservative, based on our prior experience, which reported a drop-out rate of 15%.

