Immunocap Assay: Changes in serum component proteins measured through ImmunoCAP assay will be compared between randomization groups using linear mixed effects models for data collected at baseline, week 16 and the desensitization double-blind, placebo-controlled food challenge visit. The analysis will include a random subject effect and the fixed effect of randomization assignment, time, interaction between randomization assignment and time, and age. Spline models may be considered if the curves exhibit non-linear trends. Values below the limit of detection (LOD) will be imputed as X/sqrt(x)). The linear mixed effects model has the advantage that the estimation of the model parameters will be unbiased even in the presence of missing outcomes, assuming that the missing values depend only on the observed values (missing at random). If the missing at random assumption is not plausible, pattern-mixture modeling (which stratifies subjects by their pattern of missing data) will be used.

Cell population frequency: Quantile-linear mixed effects models will be used for the frequency of %CD63+ basophil, peanut-specific Th2 cells and T cells.

BBEA Assay: The bead-based epitope assay (BBEA) protocol will be used to obtain peanut specific of 64 15-mer epitopes derived from key peanut allergens—34 from Ara h 1, 16 from Ara h 2, and 14 from Ara h. All data processing, quality control, and analyses will be performed in R (version 4.3.3; R Foundation, Vienna, Austria). Binding scores for each epitope in the IgE and IgG4 assays will be obtained via *bbeaR*. Plate effect will be assessed using Principal Variation Component Analysis along with age strata, randomization assignment, visit, the interaction between randomization assignment and visit, and participant. If Plate effect is considered to be large, ie >10% contribution to the variance, Plate will be included as a factor in all analysis. Linear mixed effects models will be fitted by using the *limma* framework– for high dimensional omic data.

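### The quality-of-life model has one random subject effect over three visits, so its arm-by-time intervals are too narrow if children differ in rate of change; the ImmunoCAP model shares this and leaves the coding of time open

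*SAP*

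**What the plan says.** **Quality of life (SAP 6.5.2.3).** The Food Allergy Quality of Life–Parental Burden score is compared between arms with a linear mixed model on three visits: baseline, week 16 and the desensitization DBPCFC. The terms are listed in full: "The analysis will include a random subject effect and the fixed effect of randomization assignment, continuous time, and their interaction". Splines may be used if the curves are non-linear, and pattern-mixture models if missing-at-random is implausible.

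**Peanut and Ara h 2 IgE and IgG4 (SAP Addendum, Immunocap Assay).** The visits are the same three: "The analysis will include a random subject effect and the fixed effect of randomization assignment, time, interaction between randomization assignment and time, and age". Here time is not described as continuous.

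Neither paragraph names a random slope, a residual covariance structure or robust standard errors.

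**Timing of the last visit.** The protocol's Table 2 puts it at week 32, 56, 64 or 72. Protocol 8.5 allows a window of up to 6 months after the due date, so it can fall at about week 98 (72 + 26).

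**Testing.** SAP 6.1: "All hypothesis testing will be conducted at the 0.05 two-sided significance level unless otherwise specified". SAP 6.6 makes no multiplicity correction for the secondary clinical endpoints and treats their p-values as descriptive. SAP 6.1 also allows an unsuitable method to be replaced by a more appropriate one.

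**The concern.** A random intercept with independent residuals implies equal correlation between every pair of visits: children may differ in level, but within an arm they all move at one rate. With three visits there are two independent within-child contrasts, one along the slope and one around it, and the model estimates one residual variance by averaging them. If slopes differ between children, the slope contrast is the more variable of the two. The arm-by-time test depends on that contrast, yet its standard error comes from the average.

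The protocol itself makes equal slopes an unlikely assumption. Its mechanistic hypotheses and secondary mechanistic objectives (2.1, 2.3) aim to predict which children will desensitize. The sample-size section assumes 55% success on ingestion and 20% stopping treatment. Starting amounts depend on baseline reaction dose (3.1.3).

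At stake are the standard errors, intervals and p-values for a secondary clinical endpoint and for primary mechanistic endpoints 1 and 2. The listed fallbacks do not help: splines change only the mean curve, and pattern-mixture models address only missing data.

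**Working it through.** **The plan's own figure.** The SAP gives no power or error rate for these models. Its only such figure concerns the primary endpoint: "A total of 72 children randomized with equal probability to the active or control arm (36 per group) provides approximately 85% power". It reproduces. The attenuated rates are 0.8 × 55% + 0.2 × 10% = 46% and 0.95 × 10% + 0.05 × 55% = 12.25%. With 36 per arm, the continuity-corrected chi-squared test has power 84.2% (Fleiss approximation) or 85.9% (exact enumeration). That calculation is not in question; it supplies the sample size used below.

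**Inputs.** From the documents: 36 per arm, two-sided 5%, visits at 0, 16 and 32–72 weeks (to about 98 with the window). Assumed, because the documents give no variances: k = (between-child slope SD × 72 weeks) / residual SD, varied from 0 to 10; intraclass correlation 0.5.

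**Closed form, continuous time, last visit at week 72 for all.** The mean visit time is (0 + 16 + 72)/3 = 29.33 weeks. The sum of squares about it is Sxx = 860.4 + 177.8 + 1820.4 = 2858.7, and Sxx/72² = 2858.7/5184 = 0.551. Let r = 0.551 k².

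- True variance along the slope, in units of residual variance: 1 + r.
- Variance the random-intercept model uses (average over the two within-child contrasts): 1 + r/2.
- Ratio of true to reported variance: (1 + r)/(1 + r/2), which tends to 2.
- Type I error: 2[1 − Φ(1.96/√ratio)].

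Example, k = 1: r = 0.551; ratio = 1.551/1.276 = 1.216; true SE is 1.10 times the reported SE; 1.96/1.103 = 1.777; type I error 7.6%.

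**Simulation.** REML random-intercept fits, 4,000 trials per setting, F test of arm-by-time. The mixes of final visits are assumed, equal in both arms.

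| k | closed form | all at wk 72 | 72/64/56/32 | 72/32 | 98/72/64/32 |
|---|---|---|---|---|---|
| 0 | 5.0% | 4.8% | 4.7% | 5.6% | 4.1% |
| 0.5 | 5.7% | 6.1% | 6.0% | 6.2% | 6.6% |
| 1 | 7.6% | 7.6% | 7.7% | 8.4% | 10.2% |
| 2 | 11.2% | 11.1% | 12.7% | 14.5% | 17.7% |
| 3 | 13.4% | 12.6% | 16.3% | 19.6% | 21.9% |
| 10 | 16.2% | 17.1% | 23.4% | 28.1% | 28.5% |

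The closed form has a ceiling of 16.6%, but only when all final visits fall at the same week. Raising the intraclass correlation to 0.8 made little difference (7.4% at k = 1, 10.3% at k = 2, all at week 72). If slopes vary in the intervention arm only, a separate run with mixed final visits gave 5.8%, 9.4% and 13.2% at k = 1, 2 and 3.

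**Analysis that allows for slope variation.** A t test on each child's own fitted slope, the simple analogue of a random slope, stayed at 4.4–5.4% in every setting. The random-slope model with Kenward-Roger degrees of freedom was not itself simulated.

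**ImmunoCAP with categorical time.**

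- Joint arm-by-visit test: 5.0%, 5.1%, 5.8%, 7.1% and 7.0% at k = 0, 1, 2, 3 and 10. It is nearly protected because it averages over the same two contrasts as the residual variance.
- Baseline-to-final contrast by arm, all at week 72: true variance 2 + k², reported variance 2(1 + r/2) = 2 + 0.551 k². At k = 1 the ratio is 3/2.551 = 1.176 and the type I error 7.1%. At k = 2 it is 6/4.206 = 1.427, giving 10.1%. At k = 5 it is 27/15.79 = 1.71, giving 13.4%. Simulation gave 6.6–14.4% for k = 1 to 5.

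**Wheal size (SAP 6.5.2.2).** Two visits leave one within-child contrast, so there is nothing to average and this mechanism does not arise.

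**The case against.** The strongest objection is that no error rate can be read off the plan. A reader might infer that both models reject a true null about 8–17% of the time. The documents do not support that. They give no SD, slope variance or correlation for these outcomes, the rate is 5% without slope variation, and it stays below 8% until the slope SD over 72 weeks reaches about 1.1 residual SDs (all final visits at week 72). Nor is 17% an upper bound, because unequal final-visit times push the rate higher. This objection stands, and the size is therefore given only as a range under stated assumptions.

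A reader might also carry the quality-of-life figures over to IgE and IgG4. The Addendum does not say time is continuous, and with categorical time the result depends on which test is used. This stands too.

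Third, the SAP says a random subject effect, whereas its transcriptomic paragraph explicitly says random intercept, so intercept-only is an inference. It is the ordinary reading, since a list of terms with one subject effect contains no slope, but the wording could be tightened without any change of intent.

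Fourth, SAP 6.1 permits a better method and SAP 6.6 makes secondary clinical p-values descriptive. Both are true, but neither settles the matter. SAP 6.1 names no check for slope variation and leaves the choice until the data are seen. SAP 6.6 does not widen the intervals, and it does not cover the mechanistic endpoints.

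**Conclusion.** The concern holds conditionally. On its ordinary reading, the quality-of-life model reports an arm-by-time standard error that is too small whenever children within an arm differ in rate of change. With a common final visit at week 72 and slopes varying in both arms, the true SE is 1.10 times the reported one at k = 1 and 1.23 times at k = 2. The corresponding type I error is 7–8% and 11–13% (the latter including final visits spread over weeks 32–72), rising to about 15–20% or more for larger variation with unequal final visits. These figures rest on assumed variances and assumed mixes of final-visit weeks.

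For ImmunoCAP there are two gaps: the same single random effect, and an unstated coding of time. The consequence ranges from mild (joint categorical test, up to about 7%) to the quality-of-life figures (continuous time).

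This should be changed, but it does not threaten the trial's main conclusion, because the primary analysis does not use these models.

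**What to change.** **SAP 6.5.2.3.** Keep continuous time, and replace the single random subject effect with a correlated random intercept and random slope for time, with Kenward-Roger degrees of freedom. This suits final visits at very different weeks better than an unstructured matrix by visit label, which would pool weeks 32 to 72 or later into one variance.

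**Addendum, Immunocap Assay.** State how time enters. If continuous, use the same random intercept and slope. If categorical, use an unstructured covariance across the three visits and name the baseline-to-final contrast by arm as the test.

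**If the model does not converge.** Use robust (sandwich) standard errors with a small-sample correction, which keeps all available data. Give the final-minus-baseline change comparison only as a check, since it drops children without a final visit.

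**Cost.** A wording change in two paragraphs and small changes to the model code before data lock. A few more covariance parameters are estimated from about 72 children, and the intervals become slightly wider. No visit, sample or procedure changes.
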